4.0 ANALYSIS VARIABLES

4.1 Primary Endpoint

The primary endpoint is the time from randomization to the first occurrence of any event in the predefined MACE composite, which includes:

- CV death.
- Non-fatal myocardial infarction (MI).
- Non-fatal stroke.
- Unstable angina with urgent coronary revascularization.

4.2 Secondary Endpoints

The secondary endpoints are:

- The time from randomization to the first occurrence of any Antiplatelet Trialists' Collaborative (APTC) event, which includes:
 - CV death.
 - Non-fatal MI.
 - Non-fatal stroke.
- The time from randomization to the occurrence of each individual event in the pre-defined MACE composite.

4.3 Additional Endpoints

The following are additional endpoints:

- The time from randomization to the first occurrence of any event in the pre-defined MACE composite plus any of the following events:
 - Urgent Cerebral revascularization [non-elective].
 - Hospitalized congestive heart failure (CHF).
 - Arrhythmias not associated with ischemia.
 - Venous and peripheral arterial thromboembolic events; eg, Deep Vein Thrombosis (DVT) and Pulmonary Embolism (PE).
 - Transient Ischemic Attack (TIA).
- The time from randomization to the occurrence of all-cause death.
- The time from randomization to the occurrence of all-cause death during treatment (from randomization to last dose of study medication).
- The time from last dose of study medication to the occurrence of all-cause death.
- Percentage of subjects whose average sUA levels from the end of the first year of treatment to the end of the study are <4.0 mg/dL, ≥4 to <5.0 mg/dL, ≥5 to <6.0 mg/dL, and ≥6.0 mg/dL.

- The mean number of flares requiring treatment from the end of the first year of treatment to the end of the study.
- Percentage of subjects with tophi resolution by the end of Years 1, 2, 3 and 4 for subjects with a primary palpable tophus at the Day 1 Visit.
- Other safety assessments will include:
 - Adverse events (including rash events),
 - Clinical laboratory evaluations (hematology, serum chemistry, and urinalysis),
 - Vital signs measurements (blood pressure and heart rate), and
 - Electrocardiogram (ECG) findings.

5.0 DETERMINATION OF SAMPLE SIZE

A total of 7500 subjects (3750 per treatment group) are planned to be enrolled in this study. The sample size will provide at least 90% power to meet a non-inferiority margin of 1.3 for the hazard ratio (febuxostat relative to allopurinol) of the primary endpoint. The sample size calculation assumed a true hazard ratio of 1.0 at a 1-sided 2.5% significance level with 3 interim analyses at approximately 25%, 50% and 75% of the events based on critical values obtained using the Lan-DeMets - O'Brien-Fleming alpha spending function.

For the determination of non-inferiority between the febuxostat treatment group and the allopurinol treatment group, the sample size calculation further assumed:

- Constant proportional hazards and exponential survival curves,
- Annual adjudicated MACE composite rate of 2.8%,
- Maximum length of participation of 5 years,
- Accrual time of 2.5 years, and
- Annual drop-out rate of 10%.

This study is designed to have a maximum of 624 MACE.

6.0 METHODS OF ANALYSIS AND PRESENTATION

6.1 General Considerations

The SAS System with the HP-Unix operating system, will be used to perform the statistical analyses. Unless otherwise specified, all statistical tests and confidence intervals (CIs) will be two-sided and conducted at the 0.05 significance level. All computations will be performed prior to rounding. Statistical significance will be determined using p-values which have been rounded to 3 decimal places. Unless otherwise specified, descriptive statistics on continuous variables will consist of the number of subjects (N), mean, standard deviation, minimum, 25th percentile, median, 75th percentile, and maximum.

For the purpose of this document study drug will refer exclusively to the double-blind treatment namely: febuxostat (40 mg QD or 80 mg QD) or allopurinol (200 mg to 600 mg QD in 100 mg increments). Unless specified otherwise all statistical tables will be presented by febuxostat and allopurinol treatment groups with no summaries by dose.

6.1.1 Baseline, Study Day, and Window Conventions

For the time to event endpoints, time to event will be the time from the date of randomization to the first occurrence of any event in the respective endpoint.

A windowing convention will be used to determine the analysis value for a given study visit and will be applicable for all by-visit summaries and analyses, unless otherwise specified. The convention to be used for the analysis of efficacy and safety is summarized in [Table 6.a](#).

Unless otherwise specified, baseline will be defined as the last observation prior to receiving the first dose of study drug on Day 1, and post-baseline values will be defined as those values collected within the specified window for that visit.

If a subject has more than one measurement in the same visit window, the measurement closest to the target day will be used. If two measurements in the same window are of equal distance to the target day, the measurement that occurs after the target day will be used. If two or more measurements occur on the same day, the last repeat value will be used.

6.2 Major Protocol Violations

No statistical analyses will be planned using the Per Protocol Set. Major protocol violations will be summarized for this study.

6.3 Analysis Sets

The primary endpoint and all other analyses by treatment group will be analyzed according to the randomized treatment using the Full Analysis Set (FAS). The FAS will consist of all subjects who were randomized and received at least one dose of double-blind study medication. If a subject reports a composite MACE after treatment discontinuation, then the reported event will be counted toward the treatment to which they were randomized.

Table 6.a Visit Windows for Efficacy and Safety Variables

Visit ID	Target Day	Window
Baseline	1	Day ≤1
Week 2	14	Days 2 to 21
Week 4	28	Days 22 to 35
Week 6	42	Days 36 to 49
Week 8	56	Days 50 to 63
Week 10	70	Days 64 to 81
Month 3	91	Days 82 to 137
Month 6	182	Days 138 to 228
Month 9	273	Days 229 to 319
Month 12	364	Days 320 to 410
Month 15	455	Days 411 to 501
Month 18	546	Days 502 to 637
Month 24	728	Days 638 to 819
Month 30	910	Days 820 to 1001
Month 36	1092	Days 1002 to 1183
Month 42	1274	Days 1184 to 1365
Month 48	1456	Days 1366 to 1547
Month 54	1638	Days 1548 to 1729
Month 60	1820	Days 1730 to 1911
Month 66	2002	Days 1912 to 2093
Month 72	2184	Days 2094 to 2275
Month 78	2366	Days 2276 to 2457
Month 84	2548	Days ≥2458

6.4 Disposition of Subjects

Subject eligibility will be summarized by number of subjects screened and by number and percentage of subjects randomized and not randomized. For subjects not randomized, the number and percentage of subjects by primary reason for not being randomized will be summarized.

Subject disposition will be summarized for each treatment group and overall based on the FAS. The number and percentage of subjects randomized but not treated, randomized subjects who completed study drug, and randomized subjects who discontinued study drug by reason for discontinuation will be summarized. In addition, the number and percentage of randomized subjects who completed planned study visits, and who discontinued the study prematurely by reason for premature discontinuation will be summarized.

The timing of premature discontinuation from study drug will also be summarized within the following intervals: Day 1 to Day 182 [Month 6], Day 183 to Day 364 [Month 12], Day 365 to Day 546 [Month 18], Day 547 to Day 728 [Month 24], Day 729 to Day 910 [Month 30],

Day 911 to Day 1092 [Month 36], Day 1093 to Day 1274 [Month 42], Day 1275 to Day 1456 [Month 48], Day 1457 to Day 1638 [Month 54], Day 1639 to Day 1820 [Month 60], Day 1821 to Day 2002 [Month 66], Day 2003 to Day 2184 [Month 72], Day 2185 to Day 2366 [Month 78], \geq Day 2367 [\geq Month 78].

In addition, the timing of premature discontinuation summary during the first 6 months will further be summarized using three month intervals: Day 1 to Day 91 and Day 92 to Day 182.

Comparisons between treatment groups of the rate of premature discontinuation will be assessed using Fisher's exact test both overall and by reason for discontinuation.

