3.2 Study Design

This is a phase 3B multicenter, randomized, double-blind, active-controlled study designed to evaluate the CV safety of febuxostat compared with allopurinol in subjects with gout and significant CV comorbidities. Approximately 7500 subjects will be randomly assigned to study drug treatment.

The overall duration of the study is dependent on the number of predefined MACE. The length of the study is expected to be approximately 9 years. The length of study participation for each subject will vary due to the event driven study design. This study is designed to have a maximum of 624 MACE.

On Study Day 1, eligible subjects will be randomized in a 1:1 ratio to receive either febuxostat once daily (QD) or allopurinol QD. Randomization will be stratified based on baseline renal function (normal renal function or mild renal impairment versus moderate renal impairment). Baseline renal function will be defined using the following criteria based on estimated creatinine clearance (eCLcr):

- Normal renal function: defined as an eCLcr ≥ 90 mL/min.
- Mild renal impairment: defined as an eCLcr 60 to 89 mL/min, inclusive.
- Moderate renal impairment: defined as an eCLcr 30 to 59 mL/min, inclusive.

where estimated creatinine clearance (eCLcr) is calculated using the Cockcroft-Gault formula corrected for ideal body weight (IBW); IBW is 50 kg for males and 45.5 kg for women, plus 2.3 kg for each inch in height >5 feet (60 inches)]:

[figure not shown]
$$eCLcr = \frac{(140 - \text{Age}[\text{yr}]) \times (\text{IBW}[\text{kg}]) (\text{women multiply by } 0.85)}{72 \times (\text{serum creatinine} [\text{mg/dL}])}$$

Subjects randomized to febuxostat will initially receive the 40 mg dose QD. Subjects will remain on 40 mg for the remainder of the study if their serum uric acid (sUA) is <6.0 mg/dL at the Week 2 Visit. If their sUA is ≥ 6.0 mg/dL at the Week 2 Visit they will receive febuxostat 80 mg QD at the Week 4 visit, and will remain on this dose for the remainder of the study.

Subjects randomized to allopurinol who have normal renal function or mild renal impairment will initially receive allopurinol 300 mg QD with the dose increased in 100 mg increments monthly until either a sUA <6.0 mg/dL or an allopurinol dose of 600 mg QD is achieved. Subjects randomized to allopurinol who have moderate renal impairment will initially receive allopurinol 200 mg QD with the dose increased in 100 mg increments monthly until either a sUA

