6.6 Study Drug Exposure and Compliance

Summaries of study drug exposure, study participation, and compliance will be presented by treatment group and based on the FAS. No inferential statistics will be presented.

A subject's extent of drug exposure will be calculated as the duration of treatment in the double-blind treatment period. Duration of study drug exposure in days will be defined as (date of last dose - date of first dose + 1). If the date of last dose is missing and a subject has discontinued from the study, then, for summary purposes, the last dose date will be estimated as the last drug dispense date plus the number of days in the dosing interval or date of last contact, whichever comes first. The study participation will begin on the day of randomization and end on the day of last contact. Duration of study participation in days will be defined as (date of last contact - date of randomization + 1). For subjects who report a MACE event after treatment discontinuation, the start date of the event will be used as the date of last contact.

Treatment duration and study participation will be summarized overall and by treatment group using descriptive statistics and subject counts at the intervals: Day 1 to Day 364 [Year 1], Day 365 to Day 728 [Year 2], Day 729 to Day 1092 [Year 3], Day 1093 to Day 1456 [Year 4], Day 1457 to Day 1820 [Year 5], Day 1821 to Day 2184 [Year 6], and \geq Day 2185 [\geq Year 6]. In addition, within each treatment group, the duration of treatment by each dose will be summarized.

Study drug compliance will be calculated and summarized with descriptive statistics and subject counts within compliance categories (<80%, 80–<90%, \geq 90%). Compliance (%) will be calculated as the number of capsules taken divided by two times the number of days on drug.

The number and percentage of subjects on the final dose and with dose adjustment from initial dosing will be summarized by treatment group. The final doses based on sUA response and by baseline renal function are summarized in [Figure 3.a](#).

The number and percentage of subjects with use of each type of prophylactic medication based on the initial dosing and dose adjustment from initial dosing will be summarized by treatment group. In addition, descriptive statistics on the total number of days (date of last dose - date of first dose + 1) of prophylactic dosing will be summarized by treatment group.

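### The only between-arm test of premature discontinuation (SAP 6.4) uses ever/never counts, so an early imbalance would be visible in the tables but have no suitable estimate or test

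*SAP*

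**What the plan says.** SAP 6.4 presents disposition by arm: "Subject disposition will be summarized for each treatment group and overall based on the FAS". It then describes timing: "The timing of premature discontinuation from study drug will also be summarized within the following intervals", in half-year bands followed by an open last band. It adds that "the timing of premature discontinuation summary during the first 6 months will further be summarized using three month intervals", namely Day 1 to 91 and Day 92 to 182. The section ends with its one inferential statement: "Comparisons between treatment groups of the rate of premature discontinuation will be assessed using Fisher's exact test both overall and by reason for discontinuation". Under SAP 6.1 the default applies: "all statistical tests and confidence intervals (CIs) will be two-sided and conducted at the 0.05 significance level".

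SAP 6.6 covers exposure: "Treatment duration and study participation will be summarized overall and by treatment group using descriptive statistics and subject counts at the intervals". It excludes inferential statistics and gives a rule for estimating a missing last-dose date. SAP 3.2 says: "The length of study participation for each subject will vary due to the event driven study design", and expects the study to run about 9 years. The SAP plans no time-to-discontinuation test, hazard ratio or curve.

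**The concern.** Stopping study drug is a dated event observed over unequal follow-up. Fisher's test on crude counts treats a stop on Day 20 like one in Year 6, and a subject followed for one year like one followed for seven. In the comparison by reason, the crude proportion also depends on how many subjects had already left for other reasons.

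The stake is interpretation. Several analyses depend on when subjects stop:

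- the sensitivity analysis that excludes MACE more than 30 days after stopping (6.12.1);
- the MACE rates per 100 patient-years of exposure (6.12.3);
- the mortality analyses during treatment and after last dose (4.3, 6.12.3), and those with and without deaths after discontinuation (6.13).

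A reader of these will ask whether the arms stopped at different times. The one planned p-value does not address that.

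**Working it through.** **The plan's own figure.** No stated figure is in dispute, but reproducing the 624 events checks the inputs. For a fixed design, 4 × (1.960 + 1.282)² / (ln 1.3)² gives 611 events. With the Table 6.c boundaries at 624 events, simulated power is 0.901. Exponential MACE at 2.8% per year and drop-out at 10% per year, with follow-up uniform on 2.5 to 5 years, give 621 to 624 events from 7500 subjects. So Section 5 implies 2.5 to 5 years of follow-up.

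**Inputs.** From SAP 5.0: 3750 per arm and "Annual drop-out rate of 10" percent. The SAP gives no study-drug discontinuation rate, so this drop-out rate is a stand-in; the hazard is λ = −ln 0.9 = 0.1054 per year. Assumed: one arm has m times that hazard for the first 6 months and the same hazard afterwards. Follow-up is 2.5 to 5 years (Section 5), or 6.5 to 9 years (assumed: 2.5-year accrual in a 9-year study). Tests are two-sided at 0.05 and unstratified; competing death and MACE are ignored.

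**Early excess, m = 1.75, follow-up 2.5 to 5 years.**

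- Stopped by Month 6: 1 − exp(−1.75 × 0.1054 × 0.5) = 8.8%, against 1 − exp(−0.1054 × 0.5) = 5.1%. The difference is 3.7 points.
- Ever stopped: 32.4% in the reference arm. In the other arm it is 1 − 0.6756 × exp(−0.75 × 0.0527) = 35.1%. The difference has shrunk to 2.6 points.
- Test on ever/never counts: standard error √[(0.351 × 0.649 + 0.324 × 0.676)/3750] = 0.0109, so z = 0.0262/0.0109 = 2.40. Approximate power is Φ(2.40 − 1.96) = 0.67. Repeated simulations of Fisher's test give about 0.65 to 0.69.
- Log-rank: observed minus expected is about 71.5 events out of a total of 2531, so z = 71.5/√(2531/4) = 2.84. Approximate power is Φ(0.88) = 0.81; simulation gives about 0.80.

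**Same excess, follow-up 6.5 to 9 years.** Ever stopped is 57.4% v 55.7%, a difference of 1.7 points with standard error 0.0114, so z = 1.50 and power is about 0.32. Simulations of Fisher's test give 0.30 to 0.32. For the log-rank test z = 71.5/√(4240/4) = 2.19 and power is 0.59, as in simulation.

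**Other patterns (simulated; 2.5 to 5 years).**

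| Pattern | Log-rank | Fisher, ever/never |
|---|---|---|
| No difference | 0.047 | 0.042 |
| Early ×1.3 | 0.20 | 0.15 |
| Early ×1.5 | 0.49 | 0.36 |
| Early ×2.0 | 0.96 | 0.89 |
| Constant hazard ratio 1.11 | 0.75 | 0.73 |
| Early ×1.75, later catch-up to about equal totals | 0.08 | 0.05 |

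**What the planned tables would show.** At m = 1.5 the Day 1 to 182 row would read 7.6% v 5.1%. A test confined to that row would reject in 99% of simulated trials, and at m = 1.75 in essentially all.

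**Shift in on-drug time.** At m = 1.75 the mean falls by about 0.11 years from 3.08, that is 0.11/3.08 = 3.6%. At m = 1.5 it falls by 0.07 years, or 2.4%.

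**The case against.** The strongest reply is that the plan already shows timing. The paragraphs directly before the Fisher sentence tabulate it, most finely in the first 6 months, and 6.6 gives duration by arm. That stands: a reader might infer that the SAP discards timing, or that early differences would go unnoticed, and the document supports neither. What remains is that the tables carry no effect estimate and no test suited to dated events.

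It is also fair to say that Fisher's test answers a legitimate question (did different proportions stop?) with sound type I error, and that nothing in the SAP is conditional on its p-value. MACE after stopping count to the randomised arm (6.3, 6.12), and subjects who stop drug are followed by phone (3.2). A reader might infer that the non-inferiority result is at risk; it is not.

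Finally, a log-rank test is no cure for every pattern. If one arm stops early and the other catches up, it is nearly as blind as Fisher's test (0.08 v 0.05). This too stands, and is why curves have to accompany the test. How often an early difference would be missed cannot be read from the SAP; it depends on the assumed multiplier.

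**Conclusion.** The point holds as a low-cost improvement. It is not an error or a contradiction in the plan. The only between-arm test of discontinuation ignores timing in a study with variable and possibly long follow-up. A time-to-event comparison had equal or better power in the early-excess, proportional and catch-up patterns examined.

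The gain is material only for an early excess that is not later reversed: about 15 points at ×1.75 on Section 5 follow-up, and nearly double the power on 6.5 to 9 years. It is about 2 points for a proportional difference on Section 5 inputs, and negligible in absolute terms if totals equalise. These sizes rest on 10% per year as a stand-in rate, assumed early multipliers, uniform accrual, and no competing events. The consequence is confined to interpreting the on-treatment and 30-day analyses.

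**What to change.** In SAP 6.4, make the between-arm comparison an analysis of time from first dose to premature study-drug discontinuation, with subjects still on drug at study end censored:

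- a log-rank test stratified by the randomisation renal stratum, with a Cox hazard ratio and 95% CI;
- cumulative incidence curves by arm, so that early or crossing differences show even where one hazard ratio would hide them;
- for each reason, the cause-specific version of the same comparison, with cumulative incidence curves.

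Keep the counts, percentages and interval table as descriptive output.

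The cost is a change of wording plus a few tables and figures from dates already collected. The small downside is that a missing last-dose date must take the estimated date of 6.6, so some stopping times will be approximate.

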6.5 Demographic and Baseline Characteristics

Demographic and baseline variables will be summarized to assess the comparability of the treatment groups by randomization. Summary statistics will be generated overall and by treatment group based on the FAS. No inferential statistics will be presented.

Descriptive statistics will be provided for continuous variables (age, height, weight, and body mass index [BMI]). The BMI (in kg/m^2) is defined as the subject's weight (in kilograms) divided by the square of their height (in meters).

The number and percentage of subjects will be presented by treatment group for categorical variables: race, ethnicity, gender, age (<65, 65–<75, \geq 75 years), BMI (<25, 25–<30, \geq 30 kg/m^2), alcohol history, smoking history, baseline renal function (moderate renal impairment, mild renal impairment, and normal renal function), and history of kidney stone, hypercholesterolemia, use of low dose aspirin, use of NSAIDs, or use of clopidogrel and other anti-platelet drugs.

Subjects' baseline renal function will be categorized as moderately impaired, mildly impaired, or normal based on their baseline estimated creatinine clearance value (eCLcr). Subjects with eCLcr values of 30 to 59 mL/min will be classified as having moderately impaired renal function, 60 to 89 mL/min as having mildly impaired renal function, and \geq 90 mL/min as having normal renal function.

In addition, summary statistics for demographic variables (Age, Gender, Ethnicity, and Race) will be provided for screen failure subjects.

6.5.1 Gout Disease History

Summaries of gout disease history will be presented by treatment group and based on the FAS. No inferential statistics will be presented.

Descriptive statistics will be provided for continuous variables (baseline serum urate, years with gout, total number of tophi at baseline, pain scale rating of last gout flare). The number and percentage of subjects will be presented by treatment group for the following categorical variables: baseline serum urate (<7.0, 7.0–<8.0, 8.0–<9.0, 9.0 –<10.0, and \geq 10.0 mg/dL), approximate number of gout flares during the past year (1 to 3, 4 to 6, and >6), time since last gout flare (<1 month ago, 1–<4 Months Ago, 4–<6 Months Ago, 6–<12 Months Ago, and \geq 1 Year Ago), use of previous urate-lowering therapy, signs and symptoms of previous gout flares (Redness, Tenderness, Swelling, Joint Warmth, and Other), pain scale rating of last gout

flare (0 (no pain), 1-5, 6-10), presence of tophus at baseline, and site of primary tophus (wrist/hand, Ankle/Foot/Toe/Instep, Elbow, Knee, and Other).

